1. PROTOCOL SYNOPSIS

Name of Sponsor/Company: Acceleron Pharma Inc. [name]
Name of Investigational Product: ACE-536
Name of Active Ingredient: Luspatercept (ACE-536)
Title of Study: An Open-Label Extension Study to Evaluate the Long-Term Effects of ACE-536 for the Treatment of Anemia in Patients with Low or Intermediate-1 Risk Myelodysplastic Syndromes (MDS) Previously Enrolled in Study A536-03
Study Centers: Up to 20
Phase of development: 2
Objectives: Primary: 
• To evaluate the long-term safety and tolerability of ACE-536 in patients with low or intermediate-1 risk MDS who were previously enrolled in study A536-03. Secondary: 
• To evaluate erythroid response (modified HI-E from International Working Group [IWG] 2006 criteria¹), defined as proportion of patients with:
○ A mean hemoglobin (Hgb) increase ≥ 1.5 g/dL over an 8-week period as compared to baseline, not influenced by red blood cell (RBC) transfusion, in non-transfusion dependent (NTD) patients.○ A decrease of ≥ 4 units or $\geq 50\%$ of units of RBCs transfused over a period of 8 weeks, relative to the 8 weeks immediately prior to Day 1, in transfusion dependent (TD) patients.• To evaluate rates of erythroid, neutrophil and platelet (HI-E, HI-N and HI-P) responses (IWG 2006 criteria)• To evaluate the rate of RBC transfusion independence lasting ≥ 8 weeks in TD patients• To evaluate time to HI-E response and duration of HI-E response (modified and non-modified IWG 2006 criteria)• To evaluate the mean change in RBC transfusion burden in TD patients and mean change in hemoglobin levels in NTD patients• To evaluate the pharmacokinetic (PK) profile of ACE-536• To evaluate other pharmacodynamic (PD) effects (e.g., iron overload/metabolism, erythropoietin (EPO), and reticulocytes)

Exploratory:

- To examine biomarkers related to the transforming growth factor beta (TGF- β) superfamily
- To examine self-reported quality of life using tools including but not limited to the Functional Assessment of Cancer Therapy-Anemia Scale (FACT-An) questionnaire

Study Design:

This open-label extension study will evaluate the safety, tolerability, and PD effects of up to 60 months of ACE-536 treatment in patients with low or intermediate-1 risk MDS previously treated with ACE-536 for up to 3 months in study A536-03.

The base study A536-03 is a phase 2, open-label, ascending dose study to evaluate the effects of ACE-536 on anemia in patients with low or intermediate-1 risk MDS who are not currently receiving treatment with an erythropoiesis-stimulating agent (ESA). A total of up to 153 patients may be enrolled in the base study A536-03 and may be eligible for study A536-05.

Consenting patients that meet the A536-05 eligibility criteria may immediately roll over from A536-03 to study A536-05. These patients will forego the Post-treatment Follow-up (PTFU) and End of Study (EOS) visit of A536-03 to begin study A536-05. For these patients, C1D1 of A536-05 may take place 28 (\pm 7) days after the last dose administered in study A536-03, which may coincide with the patient's A536-03 End of Treatment (EOT) visit. These patients will be considered "patients without treatment interruption." Patients enrolled in expansion cohorts 2 and 3 in Study A536-03 must meet the "patients without treatment interruption" criteria to be considered for the A536-05 study, unless otherwise prospectively approved by the sponsor.

Patients who complete the EOS visit for the base study A536-03 prior to C1D1 of A536-05 are considered "patients with treatment interruption." These patients will have a 28-day screening period to allow them to be re-assessed for eligibility by meeting additional inclusion criteria, as defined in [Section 9.2](#).

Patients who have completed the EOT visit for the base study A536-03 but have not reached the EOS visit (i.e., patients in the follow-up period for A536-03), may still participate, but should be treated as patients with treatment interruption and should not begin study A536-05 C1D1 until they have completed their A536-03 EOS visit so that new baseline assessments can be measured.

For patients without treatment interruption, transfusion status (NTD or TD) will carry-over from the base study A536-03. For patients with treatment interruption, transfusion status will be reassessed prior to C1D1 of study A536-05. Transfusion status for all patients is defined as follows for all patients:

- NTD patients are defined as patients who require a transfusion of < 4 units of RBCs in the 8 weeks prior to C1D1
- TD patients are defined as patients who require a transfusion of ≥ 4 units of RBCs in the 8 weeks prior to C1D1

Each TD patient will have a defined "pre-transfusion hemoglobin threshold" which will be calculated based on transfusion history and will be used for determining when to transfuse during the study. The baseline pre-transfusion hemoglobin threshold will be the mean of all documented pre-transfusion hemoglobin values during the 12 weeks prior to C1D1 of base study A536-03 for patients without treatment interruption, or prior to C1D1 of study A536-05 for patients with

treatment interruption. During treatment, if the pre-transfusion hemoglobin level is increased by ≥ 1 g/dL compared to the baseline pre-transfusion hemoglobin threshold for that patient, transfusion should be delayed by a minimum of 7 days and/or the number of units transfused should be reduced by 1 or more RBC units. Patients should not be transfused if hemoglobin is ≥ 9 g/dL unless indicated for symptoms related to anemia or other reasons at the investigator's discretion.

Patients will participate in the extension study A536-05 for approximately 8 years, including a 28-day screening period, a 60-month treatment period, and a 3-year follow-up period.

The Safety Review Team (SRT) established for study A536-03 will review safety and PD data periodically throughout study A536-05.

Starting Dose Level:

A patient without treatment interruption may continue to be dosed with ACE-536 at the same dose level administered at their last dose in study A536-03, unless a dose reduction is required based upon patient dose modification rules from study A536-05.

All patients with treatment interruption will be initially treated with ACE-536 at an assigned starting dose level of 1.0 mg/kg, which has been deemed to be safe, well tolerated, and at least minimally effective by the SRT based on data from the base study A536-03. Examples of possible starting dose levels with respective dose levels for modification (reductions and titrations) are shown in the table below for reference.

Possible Starting Dose Levels with Dose Level Modifications (Reductions and Titrations)

3 rd Dose Reduction	2 nd Dose Reduction	1 st Dose Reduction	Starting Dose Level	1 st Dose Titration	2 nd Dose Titration	3 rd Dose Titration
	0.125 mg/kg	0.25 mg/kg	0.50 mg/kg	0.75 mg/kg	1.0 mg/kg	1.33 mg/kg
0.125 mg/kg	0.25 mg/kg	0.5 mg/kg	0.75 mg/kg	1.0 mg/kg	1.33 mg/kg	1.75 mg/kg
0.25 mg/kg	0.5 mg/kg	0.75 mg/kg	1.0 mg/kg	1.33 mg/kg	1.75 mg/kg	
0.5 mg/kg	0.75 mg/kg	1.0 mg/kg	1.33 mg/kg	1.75 mg/kg		
0.75 mg/kg	1.0 mg/kg	1.33 mg/kg	1.75 mg/kg			

- Starting dose level for patients with treatment interruption is 1.0 mg/kg.
- Starting dose level for patients without treatment interruption will be last dose level administered in study A536-03 unless a dose reduction is required based upon patient dose modification rules from study A536-05.
- Patients may be titrated up and down dose levels as required per protocol to meet dose modification and titration rules.
- Patients who require more than 2 dose reductions due to an AE should be discontinued from treatment and complete the EOT, PTFU, LTFU and EOS visits.
- The maximum dose titration will not exceed 1.75 mg/kg.

Individual Dose Modification:

The following dose modification rules include parameters which may indicate when a dose delay and/or dose reduction is required. These rules should be assessed prior to each dosing. If a dose delay is required, the patient should have visits every 1 - 3 weeks to assess hematology results and adverse events (AE) until the patient is eligible to receive the next dose of ACE-536.

Observation on Dosing Day	Action	ACE-536 Dose Modification
Hemoglobin \geq 12 g/dL	Hold dose and monitor patient until hemoglobin $<$ 11 g/dL	Resume dosing once hemoglobin $<$ 11 g/dL
Hemoglobin \geq 2 g/dL increase from the previous dosing day, not attributable to RBC transfusion	Continue dosing	Reduce the dose by 1 dose level
Non-hematologic AE \geq Grade 3, at least possibly related to study drug	Hold dose and monitor patient until resolution of AE to \leq Grade 1 or baseline	Resume dosing upon resolution of the AE to \leq Grade 1 or baseline, and reduce the dose by 1 dose level ^a
\geq 50% increase in white blood cell count (WBC) compared to pre-dose WBC of previous treatment cycle and above upper limit of normal in the absence of an associated condition (e.g., infection or concomitant corticosteroid use) ^b	
Dose delay; recheck CBC, including WBC at least weekly during dose delay.
 
If WBC remains above upper limit of normal for \geq 2 consecutive weeks in absence of an associated condition (e.g., infection or concomitant corticosteroid use); continue dose delay and collect bone marrow/peripheral blood samples to assess MDS disease status.
	
Treatment may be resumed if WBC values are below upper limit of normal within 2 weeks
 
Treatment may be resumed if:
 
 Absence of disease progression per IWG response criteria for altering natural history of MDS¹ 
AND
 
 WBC values return below upper limit of normal 
Discontinue treatment if:
 
 Disease progression per IWG response criteria for altering natural history of MDS¹ 
OR
 
 WBC remain above upper limit of normal
Presence of \geq 1% blasts in peripheral blood	Dose interruption; immediately prepare peripheral blood smear for cytromorphology assessment.	
If cytromorphology assessment confirms \geq 1% blasts in the peripheral blood; discontinue treatment
 
If cytromorphology assessment determines $<$ 1% peripheral blasts are present, repeat hematology assessment.
 
 If presence of $<$ 1% blasts in peripheral blood, treatment can be resumed at next scheduled dosing cycle. If presence of \geq 1% blasts in peripheral blood; discontinue treatment

^a Patients who require more than 2 dose reductions due to an AE should be discontinued from treatment and complete the EOT, PTFU, LTFU, and EOS visits.

^b The investigator may contact the medical monitor and forward appropriate supporting documents for review and discussion prior to making decision regarding treatment discontinuation.

Individual Dose Titration for NTD Patients:

For NTD patients (with or without interruption), after C1D1, the dose level will be assessed for titration every cycle starting at C3D1 (e.g., C3D1, C4D1, C5D1, etc.). The dose level should be titrated individually for each patient not to exceed the maximum dose level evaluated in the base study A536-03 as follows:

- If hemoglobin increase from baseline is < 1.5 g/dL throughout the previous two cycles at the same dose level, the dose level will be increased by 1 dose level (unless dose modification is required).
- If hemoglobin increase from baseline is ≥ 1.5 g/dL but not sustained for at least two consecutive study measurements during the previous two cycles at the same dose level, the dose level will be increased by approximately 1 dose level (unless dose modification required).
- If hemoglobin increase from baseline is ≥ 1.5 g/dL (not influenced by RBC transfusion) as measured by two or more consecutive study measurements during the previous two cycles at the same dose level, the dose level will be unchanged (unless dose modification is required).

Baseline hemoglobin to assess titration will be the average of two or more measurements performed during the screening period for base study A536-03 (for patients without treatment interruption) or study A536-05 (for patients with treatment interruption).

Individual Dose Titration for TD Patients:

For all TD patients (with and without treatment interruption), the dose level will be assessed for titration every cycle starting at Cycle 3 Day 1 (e.g., C3D1, C4D1, C5D1, etc.). The dose level should be titrated individually for each patient not to exceed the maximum dose level evaluated in the base study A536-03 as follows:

- If patient has ≥ 1 transfusion event during the previous 2 cycles at the same dose level, the dose will be increased by 1 dose level (unless a dose modification is required).

Number of patients: A planned total of up to 153 patients who enrolled in the base study A536-03 may be eligible for the extension study A536-05.

Inclusion Criteria:

All patients must meet the following criteria:

1. Completion of the treatment period in the base study A536-03.
2. Females of child bearing potential (defined as sexually mature women who have not undergone hysterectomy or bilateral oophorectomy, or are not naturally postmenopausal ≥ 24 consecutive months) must have negative urine or blood pregnancy test prior to enrollment and use adequate birth control methods (abstinence, oral contraceptives, barrier method with spermicide, or surgical sterilization) during study participation and for 12 weeks following the last dose of ACE-536. Males must agree to use a latex condom during any sexual contact with females of child-bearing potential while participating in the study and for 12 weeks following the last dose of ACE-536, even if he has undergone a successful vasectomy. Patients must be counseled concerning measures to be used to prevent pregnancy and potential toxicities prior to dosing with ACE-536.

3. Patient is able to adhere to the study visit schedule, understand and comply with all protocol requirements.
4. Patient understands and is able to provide written informed consent.

Patients with treatment interruption (defined as patients who complete their A536-03 EOS visit) must also meet the following criteria:

5. Documented diagnosis of idiopathic/de novo MDS or non-proliferative chronic myelomonocytic leukemia (CMML) according to the World Health Organization (WHO) criteria² (white blood count [WBC] < 13,000/ μ L) that meets International Prognostic Scoring System (IPSS) classification ([Appendix 2](#)) of low or intermediate-1 risk disease as determined by microscopic and standard cytogenetic analyses of the bone marrow and peripheral complete blood count (CBC) obtained during screening;
6. Anemia defined as:
 - Mean hemoglobin concentration < 10.0 g/dL of 2 measurements (one performed within one day prior to Cycle 1 Day 1 and the other performed 7-28 days prior to Cycle 1 Day 1), for NTD patients (defined as having received < 4 units of RBCs within 8 weeks prior to Cycle 1 Day 1), OR
 - Transfusion Dependent (TD), defined as having received \geq 4 units of RBCs within 8 weeks prior to Cycle 1 Day 1.
7. Platelet count \geq 30 x 10^9 /L.
8. ECOG performance status of 0, 1, or 2 (if related to anemia).
9. Adequate renal (creatinine \leq 2.0 x upper limit of normal [ULN]) and hepatic (total bilirubin < 2 x ULN and aspartate aminotransferase (AST) and alanine aminotransferase (ALT) < 3 x ULN) function.

Exclusion Criteria:

All patients must not meet any of the following criteria:

1. Discontinuation/withdrawal from the base study A536-03 (due to patient request, patient unwillingness or inability to comply with the protocol, pregnancy, use of prohibited medication [e.g. azacitidine], medical reason or AE, disease progression, persistent increase in white blood cell count (WBC), presence of \geq 1% blasts in peripheral blood, hypersensitivity reaction to the study drug, at the discretion of the sponsor, or loss to follow-up) prior to completion of the treatment period.
2. Prior treatment with azacitidine (injectable or oral) or decitabine.
3. Treatment within 28 days prior to Cycle 1 Day 1 with:
 - ESA,
 - Granulocyte colony-stimulating factor (G-CSF) and granulocyte-macrophage colony stimulating factor (GM-CSF),
 - Lenalidomide.
4. For patients with treatment interruption only: Iron chelation therapy if initiated within 56 days prior to Cycle 1 Day 1.

5. Treatment with another investigational drug (including sotatercept [ACE-011]) or device, or approved therapy for investigational use \leq 28 days prior to Cycle 1 Day 1, or if the half-life of the previous investigational product is known, within 5 times the half-life prior to Cycle 1 Day 1, whichever is longer.
6. Major surgery within 28 days prior to Cycle 1 Day 1. Patients must have completely recovered from any previous surgery prior to Cycle 1 Day 1.
7. Known positive for human immunodeficiency virus (HIV), active infectious hepatitis B (HBV) or active infectious hepatitis C (HCV).
8. Uncontrolled hypertension defined as systolic blood pressure (SBP) \geq 150 mm Hg or diastolic blood pressure (DBP) \geq 100 mm Hg.
9. Pregnant or lactating females.
10. History of severe allergic or anaphylactic reactions or hypersensitivity to recombinant proteins or excipients in the investigational drug.
11. Any other condition not specifically noted above which, in the judgment of the investigator, would preclude the patient from participating in the study.

Investigational product, dosage and mode of administration:

ACE-536 drug product will be provided as either a sterile, liquid formulation or a lyophilized powder formulation for reconstitution with water. Each single-use vial of the liquid formulation contains 25 mg of ACE-536 in a 0.5 mL Tris-buffered saline solution (50 mg/mL).

Each single-use vial of the lyophilic formulation may contain either 25 mg, 50 mg, or 75 mg ACE-536 for reconstitution with 0.5 mL, 1 mL, or 1.5 mL water, respectively, to form a citrate-buffered solution (50 mg/mL) for injection.

ACE-536 will be administered by SC injection on Day 1 of each cycle.

Criteria for Evaluation:

Safety Assessments:

- All patients will be assessed for safety by monitoring AEs, clinical laboratory tests, vital signs, ECG, anti-drug antibody (ADA) testing, ECOG status, and physical examination.

Efficacy Assessments:

- Patients will be assessed for erythroid response over approximately 63 months following initiation of treatment. Erythroid response endpoints will be determined by monitoring hematologic laboratory values and RBC transfusions.
- Other secondary efficacy endpoints will be assessed by examining erythropoiesis, iron overload, and iron metabolism:
 - Erythropoiesis parameters include serum EPO levels, reticulocytes, nucleated RBCs and soluble transferrin receptor
 - Iron overload/metabolism parameters include serum iron, total iron binding capacity (TIBC), transferrin, soluble transferrin receptor, ferritin, and hepcidin

PK Assessments:

- Blood samples will be drawn to evaluate PK parameters.

Exploratory Assessments:

- Biomarkers related to the TGF- β superfamily

Patient-reported quality of life in the expansion cohort using tools including but not limited to the FACT-An questionnaire

Statistical Methods

Sample Size Calculation:

There is no formal sample size calculation for the study although up to 153 patients may participate from the base study A536-03 study.

Analysis Populations:

The modified Intent-to-Treat (mITT) Population: All patients enrolled in the study who received at least one dose of ACE-536.

Efficacy Evaluable (EE) Population: All patients who received at least one dose of ACE-536 and have 1) at least four hemoglobin assessments over an 8-week period post-treatment in NTD patients OR, 2) at least 8 consecutive weeks of transfusion frequency data between Cycle 1 Day 1 and EOT visit in TD patients.

Pharmacokinetics Population: All patients who received at least 1 dose of ACE-536 during Study A536-05 and have sufficient serum ACE-536 values for PK analysis.

Primary Endpoint Analysis:

Safety analysis: To assess clinical safety, AEs, vital sign measurements and clinical laboratory information will be summarized. AEs will be coded using the Medical Dictionary for Regulatory Activities (MedDRA). Changes from baseline for clinical laboratory values and vital signs will be summarized over time. Descriptive statistics and shift tables will be generated as appropriate.

Efficacy/Pharmacodynamic Effects Analysis of Secondary Endpoints:

All efficacy analyses will be performed for the EE and mITT populations.

Efficacy will be evaluated by determining the proportion of patients who have a modified HI-E erythroid response rate based upon the IWG 2006 criteria ([Appendix 5](#)), defined as 1) A mean hemoglobin increase ≥ 1.5 g/dL over an 8-week period as compared to baseline, not influenced by RBC transfusion in NTD patients or 2) A decrease of ≥ 4 units or $\geq 50\%$ of units of RBCs transfused over a period of 8 weeks, relative to the number of units of RBCs transfused in the 8 weeks immediately prior to Cycle 1 Day 1 in TD patients.

Baseline hemoglobin will be the average of two or more measures (not influenced by RBC transfusion) performed during the screening period for study A536-03 (for patients without interruption) or study A536-05 (for patients with interruption).

Baseline units of RBCs transfused will be the 8-week period prior to study A536-03 (for patients without interruption) or study A536-05 (for patients with interruption).

The erythroid response will be summarized using both a point estimate and its exact 95% confidence interval based on binomial distribution.

No direct comparison testing with concurrent or historical controls will be performed.

Analysis of other Secondary efficacy/pharmacodynamic endpoints will include:

- Time to HI-E response and duration of HI-E response as per the IWG 2006 criteria and modified IWG 2006 criteria.
- Mean RBC transfusion burden
- Rate of RBC transfusion-free period lasting \geq 8 weeks in TD patients.
- Mean hemoglobin level change in NTD patients
- Other PD endpoints including:
 - Biomarkers for iron overload/metabolism
 - Relationship of biomarkers to response
 - Rates of HI-N and HI-P

The **exploratory endpoints** will include:

- Biomarkers related to the TGF- β superfamily.
- Patient-reported quality of life using tools including but not limited to the FACT-An questionnaire

All binary endpoints will be summarized using both a point estimate and its exact confidence interval based on the binomial distribution. The time-to-event type secondary endpoints will be analyzed using Kaplan-Meier method to estimate the survival curve and median time to event and 95% confidence interval.

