10.8. Individual Dose Modification Rules

The following dose modification rules include parameters which may indicate when a dose delay and/or dose reduction is required. These rules should be assessed prior to each dosing. If a dose delay is required the patient should have visits every 1-3 weeks to assess hematology results and AEs until the patient is eligible to receive the next dose of ACE-536.

Observation on Dosing Day	Action	ACE-536 Dose Modification
Hemoglobin \geq 12 g/dL	Hold dose and monitor patient until hemoglobin $<$ 11 g/dL	Resume dosing once hemoglobin $<$ 11 g/dL
Hemoglobin \geq 2 g/dL increase from the previous dosing day, not attributable to RBC transfusion	Continue dosing	Reduce the dose by 1 dose level
Non-hematologic AE \geq Grade 3, at least possibly related to study drug	Hold dose and monitor patient until resolution of AE to \leq Grade 1 or baseline	Resume dosing upon resolution of the AE to \leq Grade 1 or baseline, and reduce the dose by 1 dose level ^a
\geq 50% increase in white blood cell count (WBC) compared to pre-dose WBC of previous treatment cycle and above upper limit of normal in the absence of an associated condition (e.g., infection or concomitant corticosteroid use) ^b	Dose delay; recheck CBC, including WBC at least weekly during dose delay.	Treatment may be resumed if WBC values are below upper limit of normal within 2 weeks
	If WBC remains above upper limit of normal for \geq 2 consecutive weeks in absence of an associated condition (eg, infection or concomitant corticosteroid use); continue dose delay and collect bone marrow/peripheral blood samples to assess MDS disease status.	Treatment may be resumed if: 
 Absence of disease progression per IWG response criteria for altering natural history of MDS¹ AND 
 WBC values return below upper limit of normal Discontinue treatment if: 
 Disease progression per IWG response criteria for altering natural history of MDS¹ OR 
 WBC remain above upper limit of normal
Presence of \geq 1% blasts in peripheral blood (based on local laboratory hematology sample)	Dose interruption; immediately prepare peripheral blood smear for cytomorphology assessment.	If cytomorphology assessment confirms \geq 1% blasts in the peripheral blood; discontinue treatment If cytomorphology assessment determines $<$ 1% peripheral blasts

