10.9. Individual Dose Titration

10.9.1. Individual Dose Titration for NTD Patients

For NTD patients (with or without interruption), after C1D1, the dose level will be assessed for titration every cycle starting at C3D1) (e.g., C3D1, C4D1, C5D1, etc.). The dose level should be titrated individually for each patient not to exceed the maximum dose level evaluated in the base study A536-03 as follows:

- If hemoglobin increase from baseline is < 1.5 g/dL throughout the previous two cycles at the same dose level, the dose level will be increased by 1 dose level (unless dose modification is required).
- If hemoglobin increase from baseline is ≥ 1.5 g/dL but not sustained for at least two consecutive study measurements during the previous two cycles at the same dose level, the dose level will be increased by approximately 1 dose level (unless dose modification required).
- If hemoglobin increase from baseline is ≥ 1.5 g/dL (not influenced by RBC transfusion) as measured by two or more consecutive study measurements during the previous two cycles at the same dose level, the dose level will be unchanged (unless dose modification is required).

Baseline hemoglobin to assess titration will be the average of two or more measurements performed during the screening period for base study A536-03 (for patients without treatment interruption) or study A536-05 (for patients with treatment interruption).

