10.10. Other Considerations for Dose Modification, Delay or Discontinuation

For individual patients judged by the investigator to be at an unacceptable risk, but who do not meet the protocol-defined conditions for a dose modification or interruption, the investigator should consult with the medical monitor to decide whether to continue dosing at the same dose level, reduce the dose level, delay the patient's dose, or discontinue the patient's treatment with ACE-536.

Patient treatment interruption for site administrative reasons will be allowed between Cycles 17 and 18 and between Cycles 35 and 36 upon discussion with the sponsor.

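### After a dose cut for a related Grade 3 or higher non-hematologic AE, the default titration rule sends the patient back to the AE dose after two cycles if the efficacy trigger is met

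*Protocol*

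**What the plan says.** **Reduction.** Under Protocol 10.8 (repeated in the synopsis), a non-hematologic AE of Grade 3 or higher, at least possibly related to study drug, leads to a hold. Dosing resumes once the AE has fallen to Grade 1 "or baseline, and reduce the dose by 1 dose level". No duration is given for the lower level. The table's first column is headed "Observation on Dosing Day", and the introduction adds: "These rules should be assessed prior to each dosing".

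**Titration.** From C3D1, titration is assessed every cycle. In 10.9.2 the trigger for a TD patient is "≥ 1 transfusion event during the previous 2 cycles at the same dose level, the dose will be increased by 1 dose level". In 10.9.1 an NTD patient whose hemoglobin rise stays below 1.5 g/dL "throughout the previous two cycles at the same dose level, the dose level will be increased by 1 dose level". A rise that reaches 1.5 g/dL but is not sustained has the same consequence. The one exception written into these rules is that a dose modification is required.

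**Limits.** Both titration sections say: "The dose level should be titrated individually for each patient not to exceed the maximum dose level evaluated in the base study A536-03". Section 10.7 caps the dose at 1.75 mg/kg and allows movement in both directions. It adds: "Patients who require more than 2 dose reductions due to an AE should be discontinued from treatment".

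**Discretion.** Section 10.10 covers patients the investigator judges to be at unacceptable risk "who do not meet the protocol-defined conditions for a dose modification or interruption, the investigator should consult with the medical monitor to decide" on the dose. Section 12.2 requires AEs to be reviewed before each dose, 10.6 has the Safety Review Team look at safety data periodically, and 9.3 allows treatment to be stopped for an AE.

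**The concern.** The reduction rule responds to toxicity and the titration rule to insufficient efficacy, and nothing in the text ranks one above the other once the AE has resolved. A site that follows the written rules would reduce the dose, wait two cycles, and then return the patient to the level at which a severe, possibly drug-related event occurred. Preventing this takes a case-by-case decision to depart from an instruction to increase.

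Long-term safety and tolerability is the primary objective, so the default should lean the other way. The gap matters most in TD patients, because a single transfusion is enough. A patient who meets the study's own modified HI-E definition, with half the baseline units, can still be directed upward. SAP 5.6 counts patients with reductions and patients with increases, but plans no summary linking an increase to an earlier AE reduction. The pattern would have to be found in the listings.

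**Working it through.** The plan states no figure on this point. The check traces the rules and then asks how often the TD trigger would be met.

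**1. Does the exception apply?** It most naturally refers to the 10.8 table. That table is assessed afresh before each dose and is keyed to what is observed that day. Dosing has resumed only because the AE is at Grade 1 or lower, or at baseline, so two cycles later the AE is no longer such an observation. The exception could be read to cover a reduction still in force, but the text does not say so.

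**2. Where does the patient end up?** The ladder in 10.7 is 0.125, 0.25, 0.5, 0.75, 1.0, 1.33 and 1.75 mg/kg. For every starting level in the table (0.5 to 1.75 mg/kg), one step down and one step up gives exactly the AE dose. Example: AE at 1.33 in cycle 5; cycles 6 and 7 at 1.0; cycle 8 at 1.33. The 1.75 mg/kg ceiling never blocks this, because the patient has already had that level.

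**3. When?** Two cycles = 2 × 21 = 42 days. With ±5 days per visit: 2 × 16 = 32 to 2 × 26 = 52 days.

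**4. How large is the step?**

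| Step (mg/kg) | Increase |
|---|---|
| 1.33 to 1.75 | 31.6% |
| 1.0 to 1.33 | 33.0% |
| 0.75 to 1.0 | 33.3% |
| 0.5 to 0.75 | 50% |
| 0.25 to 0.5; 0.125 to 0.25 | 100% |

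**5. How many re-exposures?** AE, reduction 1, re-exposure 1, AE, reduction 2, re-exposure 2, AE, third reduction needed, stop. That is at most two re-exposures. It requires the AE to recur and the trigger to be met each time, with nobody intervening.

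**6. Chance that the TD trigger is met.** Assumption: each transfusion event is 1 or 2 units. If events are Poisson, P = 1 − exp(−m), where m = (units per 56 days) × days/56 ÷ units per event. The responder goes from the TD minimum of 4 units to 2 units per 8 weeks; the non-responder stays at 4.

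| Patient | Days | Expected units | P, 1-unit events | P, 2-unit events |
|---|---|---|---|---|
| Responder | 32 | 1.143 | 0.681 | 0.435 |
| Responder | 42 | 1.5 | 0.777 | 0.528 |
| Responder | 52 | 1.857 | 0.844 | 0.605 |
| Non-responder | 32 | 2.286 | 0.898 | 0.681 |
| Non-responder | 42 | 3.0 | 0.950 | 0.777 |
| Non-responder | 52 | 3.714 | 0.976 | 0.844 |

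If events are evenly spaced instead, a responder with one 2-unit event per 56 days has 42/56 = 75% (32/56 = 57%; 52/56 = 93%). With 1-unit events every 28 days the chance is 100%, as it is for the non-responder with either event size.

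**The case against.** The strongest reply is that the protocol plans for re-escalation openly. Section 10.7 says doses may move up and down, and its next bullet sets a cumulative limit on AE reductions. Section 10.10 already provides the wanted hold: it tells the investigator to consult the medical monitor, and continuing at the same level is one of the listed outcomes. The pre-dose AE review in 12.2 is a standing instruction and comes before any increased dose. The AE must have resolved, and the patient must then complete two cycles at the lower level without a new trigger. In 14.4 the category Possible is broad, so some reductions will follow events the drug did not cause, and restoring the dose is then reasonable. Finally, the probabilities describe transfusion and say nothing about AE recurrence, and no bias in a safety summary has been shown.

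Much of this stands. Many investigators would probably hold the dose anyway, and re-escalation should not be banned. The probabilities measure only the trigger; a responder who needs no transfusion has none. The 100% steps lie at the bottom of the ladder. The SRT Charter and Investigator's Brochure, not available here, may add guidance.

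It does not remove the gap. The up-and-down sentence confirms that a return is allowed. Section 10.10 begins only once the investigator judges the risk unacceptable. The 12.2 review is mandatory but sets no hold, and the limit on reductions acts only after the AE has recurred.

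**Conclusion.** The concern holds. On its most natural reading, the protocol text orders a return to the AE dose level after two cycles whenever the efficacy trigger is met, and keeping the lower dose depends on judgement. TD patients with no transfusion event, and NTD patients with a sustained rise of at least 1.5 g/dL, have no increase ordered.

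The return can come 42 days after dosing resumes (32 to 52), with a step of 32% to 100% and at most two re-exposures. For the 4-to-2-unit responder, the TD trigger has a 53% to 78% chance in 42 days under Poisson events (44% to 84% over 32 to 52 days), or 75% to 100% if events are evenly spaced (57% to 100%). For a non-responder at 4 units it is 78% to 95% (68% to 98%), or 100% if evenly spaced. These figures rest on the assumed event sizes and spacing.

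How many patients are affected cannot be estimated. The documents give no rate for these AEs, their recurrence or discretionary holds, and 153 is only a ceiling on enrolment. This is an improvement to consider, held with medium confidence, and not a flaw that undermines the analysis.

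**What to change.** Add one sentence to 10.9.1, 10.9.2 and the synopsis:

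> A patient whose dose was reduced for a non-hematologic AE of Grade 3 or higher, at least possibly related to study drug, will not be titrated back to the dose level at which the AE occurred unless the medical monitor agrees.

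Re-escalation stays available for events that turn out not to be drug-related, through a consultation route that 10.10 already uses. All other titration is unchanged.

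The cost is a protocol amendment with ethics committee approval and regulatory submission (section 20), and perhaps slightly lower efficacy in the few patients kept one level down. No new data or analyses are needed.
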